PatGA-Genital	Proportion of patients with at least a 2-point improvement in PatGA-Genital	ITT Population: Patients with a baseline score of at least 2	Week 12 and other post-baseline visits	Logistic regression analysis using NRI	Other secondary	Primary
			Week 12 and other post-baseline visits	Fisher's exact test using NRI		Secondary

Measure	Variable	Population (Section 6.1.1)	Time Point	Analysis and Imputation Method (Sections 6.1.3 and 6.3)	Objective/ Endpoint Type	Analysis Type
DLQI	Change from baseline in DLQI total score	ITT Population	Week 12 and other post-baseline visits	MMRM	Other secondary	Primary
			Week 12 and other post-baseline visits	ANCOVA using mBOCF		Secondary
	Proportion of patients with no sexual impairment	ITT Population	Week 12 and other post-baseline visits	Logistic regression analysis using NRI	Other secondary	Primary
			Week 12 and other post-baseline visits	Fisher’s exact test using NRI		Secondary
	Proportion of patients with DLQI(0,1)	ITT Population	Week 12 and other post-baseline visits	Logistic regression analysis using NRI	Other secondary	Primary
			Week 12 and other post-baseline visits	Fisher’s exact test using NRI		Secondary
SF-36	Change from baseline in SF-36 PCS score	ITT Population	Week 12 and other post-baseline visits	ANCOVA using mBOCF	Other secondary	Secondary

Measure	Variable	Population (Section 6.1.1)	Time Point	Analysis and Imputation Method (Sections 6.1.3 and 6.3)	Objective/Endpoint Type	Analysis Type
	Proportion of patients with at least a 2.5 point improvement in SF-36 PCS	ITT Population	Week 12 and other post-baseline visits	Logistic regression analysis using NRI	Other secondary	Primary
			Week 12 and other post-baseline visits	Fisher’s exact test using NRI		Secondary
	Change from baseline in SF-36 MCS score	ITT Population	Week 12 and other post-baseline visits	ANCOVA using mBOCF	Other secondary	Secondary
	Proportion of patients with at least a 2.5 point improvement in SF-36 MCS	ITT Population	Week 12 and other post-baseline visits	Logistic regression analysis using NRI	Other secondary	Primary
			Week 12 and other post-baseline visits	Fisher’s exact test using NRI		Secondary
	Proportion of patients with at least a 5 point improvement in SF-36 individual domain scores	ITT Population	Week 12 and other post-baseline visits	Logistic regression analysis using NRI	Other secondary	Primary
			Week 12 and other post-baseline visits	Fisher’s exact test using NRI		Secondary

Measure	Variable	Population (Section 6.1.1)	Time Point	Analysis and Imputation Method (Sections 6.1.3 and 6.3)	Objective/Endpoint Type	Analysis Type
Overall PASI	Change from baseline in Overall PASI score	ITT Population: Patients with BSA \geq 10%	Week 12 and other post-baseline visits	MMRM	Exploratory	Primary
	Percentage Improvement from baseline in Overall PASI score	ITT Population: Patients with BSA \geq 10%	Week 12 and other post-baseline visits	MMRM	Exploratory	Primary
	PASI 75	ITT Population: Patients with BSA \geq 10%	Week 12 and other post-baseline visits	Logistic regression analysis using NRI	Exploratory	Primary
			Week 12 and other post-baseline visits	Fisher’s exact test using NRI		Secondary
	PASI 90	ITT Population: Patients with BSA \geq 10%	Week 12 and other post-baseline visits	Logistic regression analysis using NRI	Exploratory	Primary
			Week 12 and other post-baseline visits	Fisher’s exact test using NRI		Secondary
	PASI 100	ITT Population: Patients with BSA \geq 10%	Week 12 and other post-baseline visits	Logistic regression analysis using NRI	Exploratory	Primary
			Week 12 and other post-baseline visits	Fisher’s exact test using NRI		Secondary

Measure	Variable	Population (Section 6.1.1)	Time Point	Analysis and Imputation Method (Sections 6.1.3 and 6.3)	Objective/ Endpoint Type	Analysis Type
CAPP	Change from baseline in CAPP genital sub-index total score	ITT Population	Week 12 and other post-baseline visits	MMRM	Exploratory	Primary
Touch Avoidance NRS	Change from baseline in Touch Avoidance NRS score	ITT Population	Week 12 and other post-baseline visits	MMRM	Exploratory	Primary
Fissure, ulcer, and/or erosion in genital area	Proportion of patients with absence of fissure	ITT Population – Patients with presence of fissure	Week 12 and other post-baseline visits	Fisher’s exact test using NRI	Exploratory	Primary ^c
	Proportion of patients with absence of fissure/erosion/ulcer	ITT Population – Patients with presence of fissure, erosion, and/or ulcer at baseline	Week 12 and other post-baseline visits	Fisher’s exact test using NRI	Exploratory	Primary ^c
	Proportion of patients with absence of erosion	ITT Population – Patients with presence of erosion at baseline	Week 12 and other post-baseline visits	Fisher’s exact test using NRI	Exploratory	Primary ^c
Psoriasis in perianal or gluteal cleft area	Proportion of patients with absence of psoriasis on perianal area	ITT Population – Patients with presence of psoriasis on perianal area at baseline	Week 12 and other post-baseline visits	Fisher’s exact test using NRI	Exploratory	Primary ^c
	Proportion of patients with absence of psoriasis on gluteal cleft	ITT Population – Patients with presence of psoriasis on gluteal cleft at baseline	Week 12 and other post-baseline visits	Fisher’s exact test using NRI	Exploratory	Primary ^c

Measure	Variable	Population (Section 6.1.1)	Time Point	Analysis and Imputation Method (Sections 6.1.3 and 6.3)	Objective/Endpoint Type	Analysis Type
Psoriasis in peri-genital area	Proportion of patients with absence of psoriasis on pubis	ITT Population – Patients with presence of psoriasis on pubis at baseline	Week 12 and other post-baseline visits	Fisher’s exact test using NRI	Exploratory	Primary ^e
	Proportion of patients with absence of psoriasis on inguinal creases	ITT Population – Patients with presence of psoriasis on inguinal creases at baseline	Week 12 and other post-baseline visits	Fisher’s exact test using NRI	Exploratory	Primary ^e
Psoriasis on face, nail, scalp or axilla	Proportion of patients with absence of psoriasis on face	ITT Population – Patients with presence of psoriasis on face at baseline	Week 12 and other post-baseline visits	Fisher’s exact test using NRI	Exploratory	Primary ^e
	Proportion of patients with absence of psoriasis on nail	ITT Population – Patients with presence of psoriasis on nail at baseline	Week 12 and other post-baseline visits	Fisher’s exact test using NRI	Exploratory	Primary ^e
	Proportion of patients with absence of psoriasis on scalp	ITT Population – Patients with presence of psoriasis on scalp at baseline	Week 12 and other post-baseline visits	Fisher’s exact test using NRI	Exploratory	Primary ^e
	Proportion of patients with absence of psoriasis on axilla	ITT Population – Patients with presence of psoriasis on axilla at baseline	Week 12 and other post-baseline visits	Fisher’s exact test using NRI	Exploratory	Primary ^e

Measure	Variable	Population (Section 6.1.1)	Time Point	Analysis and Imputation Method (Sections 6.1.3 and 6.3)	Objective/ Endpoint Type	Analysis Type
Psoriasis on inframammary fold	Proportion of patients with absence of psoriasis on inframammary fold	ITT Population – Patients with presence of psoriasis on inframammary fold at baseline	Week 12 and other post-baseline visits	Fisher’s exact test using NRI	Exploratory	Primary ^e
sPGA of Genitalia and genital fissure/erosion/ulcer	Proportions of patients with absence of genital fissure, compared between two groups of patients achieving and not achieving sPGA of Genitalia (0,1) ^d	ITT Population – Patients with genital fissure at baseline	Week 12	Fisher’s exact test using NRI	Exploratory	Primary ^e
	Proportions of patients with absence of genital erosion, compared between two groups of patients achieving and not achieving sPGA of Genitalia (0,1) ^d	ITT Population – Patients with genital erosion at baseline	Week 12	Fisher’s exact test using NRI	Exploratory	Primary ^e
	Proportions of patients with absence of genital fissure/erosion/ulcer, compared between two groups of patients achieving and not achieving sPGA of Genitalia (0,1) ^d	ITT Population – Patients with genital fissure, erosion, and/or ulcer at baseline	Week 12	Fisher’s exact test using NRI	Exploratory	Primary ^e

Measure	Variable	Population (Section 6.1.1)	Time Point	Analysis and Imputation Method (Sections 6.1.3 and 6.3)	Objective/ Endpoint Type	Analysis Type
SFQ Item 1 and genital fissure/ erosion/ ulcer	Proportion of patients with SFQ Item 1 score response level, compared between two groups of patients with presence/absence of genital fissure ^d	Intent to Treat Population – Patients with genital fissure at baseline	Week 12	Fisher’s exact test	Exploratory	Primary ^e
	Proportion of patients with SFQ Item 1 score response level, compared between two groups of patients with presence/absence of genital erosion ^d	Intent to Treat Population – Patients with genital erosion at baseline	Week 12	Fisher’s exact test	Exploratory	Primary ^e
	Proportion of patients with SFQ Item 1 score response level, compared between two groups of patients with presence/absence of genital fissure, erosion, and /or ulcer ^d	Intent to Treat Population – Patients with genital fissure, erosion, and/or ulcer at baseline	Week 12	Fisher’s exact test	Exploratory	Primary ^e
SFQ Item 1 and psoriasis in perianal/ gluteal cleft area	Proportion of patients with SFQ Item 1 score response level, compared between two groups of patients with	Intent to Treat Population – Patients with psoriasis in perianal and/or gluteal cleft area at baseline	Week 12	Fisher’s exact test	Exploratory	Primary ^e

Measure	Variable	Population (Section 6.1.1)	Time Point	Analysis and Imputation Method (Sections 6.1.3 and 6.3)	Objective/Endpoint Type	Analysis Type
	presence/absence of psoriasis in perianal /gluteal cleft area ^d					
SFQ Item 1 and facial psoriasis	Proportion of patients with SFQ Item 1 score response level, compared between two groups of patients with presence/absence of facial psoriasis ^d	Intent to Treat Population – Patients with facial psoriasis at baseline	Week 12	Fisher’s exact test	Exploratory	Primary ^c
SFQ Item 2 and genital fissure/ erosion/ ulcer	Proportion of patients with SFQ Item 2 score of 0 or 1, compared between two groups of patients with presence/ absence of genital fissure ^d	Intent to Treat Population – Patients with SFQ Item 2 score ≥ 2 and with genital fissure at baseline	Week 12	Fisher’s exact test using NRI	Exploratory	Primary ^c
	Proportion of patients with SFQ Item 2 score of 0 or 1, compared between two groups of patients with presence/absence of genital erosion ^d	Intent to Treat Population – Patients with SFQ Item 2 score ≥ 2 and with genital erosion at baseline	Week 12	Fisher’s exact test using NRI	Exploratory	Primary ^c
	Proportion of patients with SFQ Item 2 score of 0 or 1, compared between two	Intent to Treat Population – Patients with SFQ Item 2 score ≥ 2 and	Week 12	Fisher’s exact test using NRI	Exploratory	Primary ^c

Measure	Variable	Population (Section 6.1.1)	Time Point	Analysis and Imputation Method (Sections 6.1.3 and 6.3)	Objective/ Endpoint Type	Analysis Type
	groups of patients with presence/absence of genital fissure, erosion, and /or ulcer ^d	with genital fissure, erosion, and/or ulcer at baseline				
SFQ Item 2 and psoriasis in perianal/gluteal cleft area	Proportion of patients with SFQ Item 2 score of 0 or 1, compared between two groups of patients with presence/absence of psoriasis in perianal/gluteal cleft area ^d	Intent to Treat Population – Patients with SFQ Item 2 score ≥ 2 and psoriasis in perianal and/or gluteal cleft area at baseline	Week 12	Fisher’s exact test using NRI	Exploratory	Primary ^e
SFQ Item 2 and facial psoriasis	Proportion of patients with SFQ Item 2 score of 0 or 1, compared between two groups of patients with presence/absence of facial psoriasis ^d	Intent to Treat Population – Patients with SFQ Item 2 score ≥ 2 and facial psoriasis at baseline	Week 12	Fisher’s exact test using NRI	Exploratory	Primary ^e
GPSIS Avoidance Subscale and facial psoriasis	Proportion of patients with a subscale score of 1 or 2, compared between two groups of patients with presence/absence of facial psoriasis ^d	Intent to Treat Population – Patients with GPSIS Avoidance Subscale Score ≥ 3 and facial psoriasis at baseline	Week 12	Fisher’s exact test using NRI	Exploratory	Primary ^e

Measure	Variable	Population (Section 6.1.1)	Time Point	Analysis and Imputation Method (Sections 6.1.3 and 6.3)	Objective/Endpoint Type	Analysis Type
GPSIS Avoidance Subscale and genital fissure/erosion/ulcer	Proportion of patients with a subscale score of 1 or 2, compared between two groups of patients with presence/absence of genital fissure ^d	ITT population – Patients with GPSIS Avoidance Subscale Score ≥ 3 and genital fissure at baseline	Week 12	Fisher’s exact test using NRI	Exploratory	Primary ^e
	Proportion of patients with a subscale score of 1 or 2, compared between two groups of patients with presence/absence of genital erosion ^d	ITT population – Patients with GPSIS Avoidance Subscale Score ≥ 3 and genital erosion at baseline	Week 12	Fisher’s exact test using NRI	Exploratory	Primary ^e
	Proportion of patients with a subscale score of 1 or 2, compared between two groups of patients with presence/absence of genital fissure/erosion/ulcer ^d	ITT population – Patients with GPSIS Avoidance Subscale Score ≥ 3 and genital fissure, erosion, and/ or ulcer at baseline	Week 12	Fisher’s exact test using NRI	Exploratory	Primary ^e
GPSIS Avoidance Subscale and psoriasis in perianal/gluteal cleft area	Proportion of patients with a subscale score of 1 or 2, compared between two groups of patients with presence/absence of	ITT population – Patients with GPSIS Avoidance Subscale Score ≥ 3 and psoriasis in perianal and/or gluteal	Week 12	Fisher’s exact test using NRI	Exploratory	Primary ^e

Measure	Variable	Population (Section 6.1.1)	Time Point	Analysis and Imputation Method (Sections 6.1.3 and 6.3)	Objective/ Endpoint Type	Analysis Type
	psoriasis in perianal/gluteal cleft area ^d	cleft area at baseline				
GPSIS Impact Subscale and genital fissure/erosion/ulcer	Proportion of patients with a subscale score of 1 or 2, compared between two groups of patients with presence/absence of genital fissure ^d	ITT population – Patients with GPSIS Impact Subscale Score ≥ 3 and genital fissure at baseline	Week 12	Fisher’s exact test using NRI	Exploratory	Primary ^e
	Proportion of patients with a subscale score of 1 or 2, compared between two groups of patients with presence/absence of genital erosion ^d	ITT population – Patients with GPSIS Impact Subscale Score ≥ 3 and genital erosion at baseline	Week 12	Fisher’s exact test using NRI	Exploratory	Primary ^e
	Proportion of patients with a subscale score of 1 or 2, compared between two groups of patients with presence/absence of genital fissure/erosion/ulcer ^d	ITT population – Patients with GPSIS Impact Subscale Score ≥ 3 and genital fissure, erosion, and/or ulcer at baseline	Week 12	Fisher’s exact test using NRI	Exploratory	Primary ^e

Measure	Variable	Population (Section 6.1.1)	Time Point	Analysis and Imputation Method (Sections 6.1.3 and 6.3)	Objective/ Endpoint Type	Analysis Type
GPSIS Impact Subscale and psoriasis in perianal/gluteal cleft area	Proportion of patients with a subscale score of 1 or 2, compared between two groups of patients with presence/absence of psoriasis in perianal/gluteal cleft area ^d	ITT population – Patients with GPSIS Impact Subscale Score ≥ 3 and psoriasis in perianal and/or gluteal cleft area at baseline	Week 12	Fisher’s exact test using NRI	Exploratory	Primary ^e
DLQI and genital fissure/erosion/ulcer	Proportion of patients with DLQI (0,1), compared between two groups of patients with presence/absence of genital fissure ^d	Intent to Treat Population – Patients with genital fissure at baseline	Week 12	Fisher’s exact test using NRI	Exploratory	Primary ^e
	Proportion of patients with SFQ Item 2 score of 0, compared between two groups of patients with presence/absence of genital erosion ^d	Intent to Treat Population – Patients with genital erosion at baseline	Week 12	Fisher’s exact test using NRI	Exploratory	Primary ^e
	Proportion of patients with SFQ Item 2 score of 0, compared between two groups of patients with presence/absence of genital fissure, erosion, and /or	Intent to Treat Population – Patients with genital fissure, erosion, and/or ulcer at baseline	Week 12	Fisher’s exact test using NRI	Exploratory	Primary ^e

Measure	Variable	Population (Section 6.1.1)	Time Point	Analysis and Imputation Method (Sections 6.1.3 and 6.3)	Objective/ Endpoint Type	Analysis Type
	ulcer ^d					
DLQI and psoriasis in perianal/ gluteal cleft area	Proportion of patients with DLQI (0,1), compared between two groups of patients with presence/absence of psoriasis in perianal/gluteal cleft area ^d	Intent to Treat Population – Patients with psoriasis in perianal and/or gluteal cleft area at baseline	Week 12	Fisher’s exact test using NRI	Exploratory	Primary ^c
DLQI and facial psoriasis	Proportion of patients with DLQI (0,1), compared between two groups of patients with presence/absence of facial psoriasis ^d	Intent to Treat Population – Patients with facial psoriasis at baseline	Week 12	Fisher’s exact test using NRI	Exploratory	Primary ^c
SF-36 MCS and genital fissure/ erosion/ ulcer	Proportion of patients with SF-36 MCS ≥ 2.5 improvement, compared between two groups of patients with presence/absence of genital fissure ^d	Intent to Treat Population – Patients with genital fissure at baseline	Week 12	Fisher’s exact test using NRI	Exploratory	Primary ^c
	Proportion of patients with SF-36 MCS ≥ 2.5 improvement, compared between	Intent to Treat Population – Patients with genital erosion at baseline	Week 12	Fisher’s exact test using NRI	Exploratory	Primary ^c

Measure	Variable	Population (Section 6.1.1)	Time Point	Analysis and Imputation Method (Sections 6.1.3 and 6.3)	Objective/ Endpoint Type	Analysis Type
	two groups of patients with presence/absence of genital erosion ^d					
	Proportion of patients with SF-36 MCS ≥ 2.5 improvement, compared between two groups of patients with presence/absence of genital fissure, erosion, and /or ulcer ^d	Intent to Treat Population – Patients with genital fissure, erosion, and/or ulcer at baseline	Week 12	Fisher’s exact test using NRI	Exploratory	Primary ^e
SF-36 MCS and psoriasis in perianal/ gluteal cleft area	Proportion of patients with SF-36 MCS ≥ 2.5 improvement, compared between two groups of patients with presence/absence of psoriasis in perianal/gluteal cleft area ^d	Intent to Treat Population – Patients with psoriasis in perianal and/or gluteal cleft area at baseline	Week 12	Fisher’s exact test using NRI	Exploratory	Primary ^e
SF-36 MCS and facial psoriasis	Proportion of patients with SF-36 MCS ≥ 2.5 improvement, compared between two groups of patients with presence/absence of facial psoriasis ^d	Intent to Treat Population – Patients with facial psoriasis at baseline	Week 12	Fisher’s exact test using NRI	Exploratory	Primary ^e

- a Patients should complete the scales in the following order: 1. GPSS, 2. GPSIS, and 3. SFQ. An e-diary will be used to collect GPSS daily, GPSIS and SFQ weekly, up to Week 12 (Visit 7); thereafter, patients will answer these questions only at scheduled study visits. At Week 12 (Visit 7), patients will complete these scales on site before completion of any other assessments.
- b The scores at each post-baseline visit for GPSS, GPSIS and SFQ, in the Blinded Treatment Period and Open-Label Treatment Period, are defined in Table.RHBQ.6.4.
- c The scores at each calendar week in the Blinded Treatment Period, for GPSS, GPSIS and SFQ, are defined in Table.RHBQ.6.4.
- d The variables are derived based on all patients in the analysis population, not for placebo or ixekizumab treated patients separately.
- e The Primary Method for this analysis is the Fisher's exact test instead of the logistic regression model.

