2.2. Study Rationale

Ixekizumab (LY2439821) is a humanized immunoglobulin G subclass 4 (IgG4) monoclonal antibody designed and engineered to selectively inhibit interleukin-17A (IL-17A). It binds with high affinity (<3 pM) and specificity to IL-17A, a proinflammatory cytokine. Neutralization of IL-17A by ixekizumab has been shown to reduce excess keratinocyte proliferation and activation (Krueger et al. 2012). Ixekizumab does not bind to ligands IL-17B, IL-17C, IL-17D, IL-17E, or IL-17F.

Phase 3 clinical trials of ixekizumab therapy were completed in patients with moderate-to-severe plaque psoriasis with percentage of body surface area (BSA) $\geq 10\%$. Ixekizumab was highly efficacious in these trials as evidenced by over 80% of patients achieving at least a 75% reduction in their Psoriasis Area and Severity Index (PASI) from baseline (PASI 75) and over one-third having complete resolution of psoriatic plaques (PASI 100) by Week 12 using a dosing regimen of 80 mg every 2 weeks following a 160-mg starting dose (Griffiths et al. 2015). In addition, patients with moderate-to-severe plaque psoriasis who were treated with ixekizumab in these studies reported significant improvements as early as Week 2 in sexual difficulties compared to placebo as measured by Question 9 of the DLQI. Thus, it is likely that ixekizumab is effective in the genital region in patients with a baseline BSA $\geq 10\%$ and may lead to improvement in sexual function in these patients. The most significant unmet medical need is in patients with BSA <10% who have moderate-to-severe genital psoriasis and limited treatment options because of the limitations of topical and phototherapy treatments for genital psoriasis described in Section 2.1.

Based on the Phase 3 psoriasis clinical trial outcomes, ixekizumab therapy in patients with moderate-to-severe genital psoriasis could address an unmet patient need and a clinical research gap identified by the dermatology community and the American Academy of Dermatology Psoriasis

Guidelines of Care Working Group (Ryan et al. 2014). One subcutaneous (SC) ixekizumab regimen will be explored: a 160-mg starting dose followed by 80 mg every 2 weeks (Q2W) for 12 weeks, and then 80 mg every 4 weeks (Q4W) with the opportunity to step up to Q2W (Section 6.1). The efficacy and safety profile of this ixekizumab dosing regimen was established in previous Phase 3 clinical studies of patients with moderate-to-severe plaque psoriasis.

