mGPASI	The Modified Genital Psoriasis Area and Severity Index (mGPASI) measure is the clinician’s determination of the patient’s psoriasis severity in the genital region (labia majora, labia minora, and perineum in females; penis, scrotum, and perineum in males) at a given time point yielding an overall score of 0 for no psoriasis to 72 for the most severe disease. The scoring index incorporates the degree of erythema (or redness (R)), induration (or thickness (T)), and scaling (S) of the genital plaques as well as erosion, fissure, and/or ulcer as a product of the genital area involved. Severity is rated for each	mGPASI score	The composite mGPASI score is calculated by summing the individual severity scores for erythema, induration and scaling / erosion, fissure, and/or ulcer, and then multiplying the sum by the area-of-involvement score as follows: $\text{mGPASI} = (R + T + S)A$ Where, R = Redness score T = Thickness score S = Scaling / Erosion, fissure and/or ulcer score A = numerical value translation of % area of psoriatic involvement scores mGPASI scores are treated as a continuous score.	If any individual component score is missing, then the mGPASI score will not be calculated, and hence mGPASI score will be missing

Measure	Description	Variable	Derivation	Imputation Approach if Components are Missing
	characteristic on a 0 to 4 scale (0 for no involvement up to 4 for severe involvement including erosion, fissure, and/or ulcer). 0 = none 1 = slight 2 = moderate 3 = severe 4 = very severe The area of involvement for the entire genital area, excluding the inguinal area, is graded on a 0 to 6 scale (0 for no involvement; up to 6 for 90% to 100% involvement). 0 = 0% (clear) 1 = 1% – 9% 2 = 10% – 29% 3 = 30% – 49% 4 = 50% – 69% 5 = 70% – 89% 6 = 90% – 100%	Change from baseline in mGPASI	$\text{Change from baseline} = \text{Observed mGPASI} - \text{Baseline mGPASI}$ A negative change indicates improvement and a positive change indicates deterioration of the condition.	Missing if baseline mGPASI or observed mGPASI value is missing

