Overall PASI	
The overall Psoriasis Area and Severity Index (PASI): combines assessments of the extent of body surface involvement in 4 anatomical regions (head and neck, trunk, arms, and legs) and the severity of scaling (S), redness (R), and plaque induration/infiltration (thickness, T) in each region, yielding an overall score of 0 for no psoriasis to 72 for the most severe disease (Fredriksson and Pettersson 1978). Severity is rated for each index (R, S, T) on a 0-4 scale (0 for no involvement up to 4 for severe involvement):
 
0 = none 1 = slight 2 = moderate 3 = severe 4 = very severe
 
The body is divided into four anatomical regions comprising the head (h), upper limb (u), trunk (t), and lower limb (l). In each of these areas, the fraction of total body surface area affected is graded on a 0-6 scale (0 for
	Overall PASI total score	
The composite overall PASI score is calculated by multiplying the sum of the individual severity scores for each area by the weighted area-of-involvement score for that respective area, and then summing the four resulting quantities as follows:
 
Overall PASI $= 0.1(R_h + T_h + S_h)A_h + 0.2(R_u + T_u + S_u)A_u + 0.3(R_t + T_t + S_t)A_t + 0.4(R_l + T_l + S_l)A_l$
 
Where, R_h, R_u, R_t, R_l = redness score of plaques on the head, upper limb, trunk, and lower limb, scored 0-4 respectively; T_h, T_u, T_t, T_l = thickness score of plaques on the head, upper limb, trunk, and lower limb, scored 0-4 respectively; S_h, S_u, S_t, S_l = scaling score of plaques on the head, upper limb, trunk, and lower limb, scored 0-4 respectively; A_h, A_u, A_t, A_l = numerical value translation of % area of psoriatic involvement score for the head, upper limb, trunk, and lower limb, respectively.
 
PASI scores are treated as a continuous score, with 0.1 increments within these values.
	If any individual component score is missing, then the overall PASI total score will not be calculated, and hence overall PASI total score will be missing

Measure	Description	Variable	Derivation	Imputation Approach if Components are Missing

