	no involvement; up to 6 for 90% - 100% involvement): 0 = 0% (clear) 1 = >0% to <10% 2 = 10% to <30% 3 = 30% to <50% 4 = 50% to <70% 5 = 70% to <90% 6 = 90% to 100% The various body regions are weighted to reflect their respective proportion of body surface area.	Overall PASI change from baseline	Calculated as: $\text{Change from baseline} = \text{Observed PASI Total} - \text{Baseline PASI Total}$ A negative change indicates improvement and a positive change indicates deterioration of the condition.	Missing if baseline PASI Total or observed PASI Total score is missing
		Overall PASI percent improvement from baseline	Calculated as: $\text{Percent improvement from baseline} = -100 * \left[\frac{\text{Observed PASI Total} - \text{Baseline PASI Total}}{\text{Baseline PASI}} \right]$ A positive % change indicates improvement and a negative % change indicates deterioration of the condition.	Missing if baseline PASI Total or observed PASI Total score is missing
		PASI75	At least a 75% improvement in PASI score from baseline	Missing if baseline PASI Total or observed PASI Total score is missing
		PASI90	At least a 90% improvement in PASI score from baseline	Missing if baseline PASI Total or observed PASI Total score is missing
		PASI100	A 100% improvement in PASI score from baseline	Missing if baseline PASI Total or observed PASI Total score is missing

Table RHBQ.6.4. Description and Derivation of Patient Reported Assessments and Health Outcome Variables

Measure	Description	Variable	Derivation	Imputation Approach if Components are Missing

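### The missing-component rule for mGPASI and overall PASI has no exception for an area score of 0, so a product known to be 0 can be set to missing

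*SAP*

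**What the plan says.** SAP Section 6.10, Table RHBQ.6.3, builds mGPASI by adding three severity scores (redness, thickness, and scaling or erosion/fissure/ulcer) and "multiplying the sum by the area-of-involvement score". The area grade is described as "0 for no involvement; up to 6 for 90% to 100% involvement", and each severity grade as "0 for no involvement up to 4 for severe involvement including erosion, fissure, and/or ulcer". The rule for blanks is: "If any individual component score is missing, then the mGPASI score will not be calculated, and hence mGPASI score will be missing".

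Overall PASI is formed by "multiplying the sum of the individual severity scores for each area by the weighted area-of-involvement score for that respective area" and summing over four regions. Its rule is the same: "If any individual component score is missing, then the overall PASI total score will not be calculated". The PASI 75, 90 and 100 variables each carry the entry "Missing if baseline PASI Total or observed PASI Total score is missing". Neither row makes an exception for an area score of 0.

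SAP Section 6.3.1 (NRI) counts a missing response as a treatment failure. Table RHBQ.6.5 assigns the methods:

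- PASI 75/90/100 are exploratory, limited to baseline BSA of at least 10%, and analysed by logistic regression with NRI.
- Change in mGPASI is an other secondary endpoint, with MMRM as its primary method and ANCOVA with mBOCF as support.

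**The concern.** A score that the SAP's own formula determines should not be recorded as unknown. With area 0, the severity items cannot change the mGPASI or that region's PASI term. Yet one blank severity item deletes the mGPASI, and one blank item in one clear region deletes the PASI total for all four regions.

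If such blanks occur after baseline, they can occur only where skin is clear, and there are more such sites in the arm with more clearance. A patient clear in every region could then be a PASI 100 failure while counting as a success on the single-item overall sPGA (0). For mGPASI, whether the value is missing would depend on the value itself, which the missing-at-random assumption behind MMRM does not cover.

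**Working it through.** **1. Formula check.** mGPASI = (R + T + S) × A, with R, T, S from 0 to 4 and A from 0 to 6. The largest value is (4 + 4 + 4) × 6 = 72, the maximum that the SAP states, so the formula is being read as intended.

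**2. Area 0.** There are 5 × 5 × 5 = 125 combinations of R, T and S. With A = 0 all 125 give 0, so the score is known with any or all severity items blank. In PASI, a region with A = 0 contributes 0 whatever its weight, and four such regions give a total of 0, which meets PASI 100.

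**3. The written rule.** mGPASI has 4 components and PASI has 4 × 4 = 16. Any blank among them makes the score missing, including a severity item whose multiplier is 0.

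**4. Consequence by endpoint.**

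- mGPASI change (Week 12, and over time to Week 52): the observation is lost at that visit. The patient's other visits stay in the MMRM.
- PASI 75/90/100, post-baseline blank: the response is missing, and NRI makes it a failure at that visit.
- PASI, baseline blank in an uninvolved region: change from baseline is missing at every visit, so the patient fails PASI 75/90/100 throughout. Uninvolved regions at baseline should be balanced by randomisation. If such blanks are unrelated to later response, they scale both arms' response rates by the same factor in expectation: the difference shrinks, but the loss is not concentrated in one arm.
- mGPASI baseline: essentially not exposed, because entry requires sPGA of Genitalia of at least 3.

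**5. Illustration for PASI 100.** Inputs:

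- 73 patients per arm (SAP 5.3), about 60% with BSA of at least 10% (SAP 6.2): 73 × 0.60 ≈ 44 ixekizumab patients.
- True PASI 100 rate of 1/3, taken from Protocol 2.2 on the earlier Phase 3 trials ("over one-third having complete resolution of psoriatic plaques (PASI 100) by Week 12").
- f, the share of fully clear patients with at least one blank severity item. **This is an assumption; the documents give no value.**

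Analysed rate = (1/3) × (1 − f). Patients lost = 44 × (1/3) × f = 14.7 × f.

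| f | Analysed PASI 100 | Loss (points) | Patients lost |
|---|---|---|---|
| 0% | 33.3% | 0 | 0 |
| 5% | 31.7% | 1.7 | 0.7 |
| 10% | 30.0% | 3.3 | 1.5 |
| 25% | 25.0% | 8.3 | 3.7 |

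With the area-0 exception the rate is 33.3% for every f. Against an assumed 1% placebo rate and 44 per arm, power of a two-sided Fisher's exact test at 0.05 is 0.995 at f = 0, 0.985 at f = 10% and 0.939 at f = 25%, so even a sizeable f would mainly distort the estimate.

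**The case against.** The strongest reply is that a blank at a clear site may never occur. Both scales define severity 0 for an uninvolved site (Table RHBQ.6.3; Protocol 8.1.2.1.1 for mGPASI), so a clear site has a recordable value and a blank would be a data-entry omission. Where the SAP expects legitimate blanks it says so, as for the GPSIS Impact Subscale and DLQI item 7 in Table RHBQ.6.4. Its silence here is consistent with severity items always being completed. Protocol 10.2 also commits the sponsor to computer edit checks and a database quality review.

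Most of this stands. No text says that severity items are skipped when area is 0, and no blank rate can be taken from the documents. It does not remove the gap, however. General edit checks are not a statement that these fields are mandatory or auto-filled, and the efficacy entries under missing data in Table RHBQ.6.2 cover only the two sPGA scores. The rule as written gives the wrong result whenever the blank does occur.

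A reader might infer that cleared patients will lose their scores and that the trial is therefore biased against ixekizumab. The documents do not support that. The direction applies only to post-baseline blanks, and only if they happen. Nor does a patient with a blank Week 12 mGPASI leave the mGPASI analysis, since the MMRM keeps that patient's other visits.

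**Conclusion.** The point holds as a gap in the derivation rule and is of low priority. Table RHBQ.6.3 sets mGPASI and PASI to missing in a case where its own formulas give the answer, and for PASI 75/90/100 the NRI rule then converts a known response into a failure.

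The size depends entirely on how often severity items are blank when area is 0. It is nil if the eCRF forces or auto-fills 0. At assumed blank rates of 5% to 10% it is about 1 to 2 of roughly 44 ixekizumab patients on PASI 100. Post-baseline blanks would work against the arm with more clearance, so they could not by themselves create a false finding for ixekizumab.

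It would be wrong to infer any threat to the confirmatory results. The primary endpoint and first major secondary endpoint are single-item sPGA scores, the other two gated tests use the itch NRS and SFQ Item 2, and the sample-size calculation does not involve mGPASI or PASI.

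**What to change.** In Table RHBQ.6.3, replace the missing-component entries with: if the area score is 0, the mGPASI (or that region's PASI term) is 0 regardless of blank severity items; otherwise the score is missing if any component is missing. Apply it at baseline and at every later visit.

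This evaluates the SAP's formula and imputes nothing uncertain. It costs one sentence and one line of derivation code. If the eCRF already requires or auto-fills 0, saying so in the table would serve equally well. Either statement should be in place before unblinding, so that the handling of blanks at clear sites is not chosen with the results in view.
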